12.1 Source Documents and Background Data

The investigator shall supply the sponsor on request with any required background data from the study documentation or clinic records. This is particularly important when data requires clarification. In case of special problems/and or governmental queries or requests for audit inspections, it is also necessary to have access to the complete study records, provided that subject confidentiality is protected.

All forms should be typed or filled out using indelible ink, and must be legible. Errors should be crossed out but not obliterated, the correction inserted, and the change initialed and dated by the investigator or his/her authorized delegate.

12.2 Audits and Inspections

The investigator should understand that source documents for this trial should be made available to appropriately qualified personnel from the Regenesis Biomedical, Inc. Quality Assurance Unit or its designees or to health authority inspectors after appropriate notification. The verification of the data must be by direct inspection of source documents and patient charts.

13. MONITORING THE STUDY

It is understood that the responsible Regenesis Biomedical, Inc. monitor (or designee) will contact and visit the investigator regularly and will be allowed, upon request, to inspect the various records of the trial (source documents and other pertinent data) provided that subject confidentiality is maintained in accord with local requirements.

It will be the monitor's responsibility to inspect the patient charts at regular intervals throughout the study to verify the adherence to the protocol and the completeness, consistency and accuracy of the data. The monitor should have access to laboratory test reports and other subject records needed. The investigator (or his/her designee) agrees to cooperate with the monitor to ensure that any problems detected in the course of these monitoring visits are resolved.

14. CONFIDENTIALITY OF TRIAL DOCUMENTS AND SUBJECT RECORDS

The investigator must assure that subjects' anonymity will be maintained and that their identities are protected from unauthorized parties. On documents submitted to the sponsor, subjects should not be identified by their names, but by an identification code. The investigator should keep a subject enrollment log showing codes, names and addresses. The investigator should maintain documents not for submission to Regenesis Biomedical, Inc., e.g., subjects' written consent forms, in strict confidence.

Study Day	-15		0	7 (+2)	30 (±3)	60 (±3)	90 (±3)	121 (±3)	150 (±3)	180 (±3)	210 (±3)	240 (±3)	270 (±3)	300 (±3)	330 (±3)	361 (±3)
Informed Consent	Х															
Demographic Information	Х															
Medical/Surgical History/Physical Exam	Х		X ³												1	
Inclusion/Exclusion Criteria	Х		X^1													
Baseline Health Economics	Х															
Pain Score Assessment (NPRS)	Х		X^2													
Measurement of Foot Thickness, Width, and Length	Х															
Height and Weight	Х							X ⁵							P	X ⁵
Urine Pregnancy Test	X^4															
Measure HbA1c	Х							Х								
Obtain Ankle-Brachial Index & Assess Venous Insufficiency	Х															
ePRO Diary (pain scores, analgesic use)		Х	Х	Х	Х	Х	Х	Х		Х		Х		Х		Х
Assess Adherence to treatment regimen and ePRO entries			X ⁷	X	Х	Х	Х	Х	Х	X ⁸						
Toronto Clinical Neuropathy Scoring System	Х							Х								Х
Randomize and Dispense Study Device			Х													
3mm Skin Punch Biopsy at distal leg and distal thigh			Х					Х								Х
WPAIQ			Х			Х		Х								
NeuroQoL Questionnaire			Х			Х		Х				Х				Х
Skin Perfusion Pressure (SPP)			Х			Х		Х								
Quantitative Sensory Test (QST) thermal			Х					Х				Х				Х
Sural Nerve Conduction Studies (NCS)			Х					Х								Х
Study Device Training			Х													
Assess Biopsy Treatment Site				Х												
Study Device Blinding Assessment				Х				Х								
Assess Adverse Events			X ⁶	X ⁶	X ⁶	X ⁶	X ⁶	X ⁶	X ⁶	X ⁶	X ⁶	X ⁶	X ⁶	X ⁶	X ⁶	X ⁶
Assess Concomitant Medications			Х	Х	Х	Х	Х	Х	Х	Х	Х	Х	Х	Х	Х	Х
Patient Global Impression (PGI)					Х	Х	Х	Х				Х				Х
Review Device Usage Report				X	Х	X	X	Х	Х	Х	Х	Х	Х	Х	Х	Х
Treatment Satisfaction					Х	Х	Х	Х				Х				Х
Return Study Device								Х								Х
Enroll Subject in Part B of protocol in ePRO and dispense device								Х								

1. Inclusion/Exclusion criteria must be reviewed to ensure patient continues to qualify for the study.

Average pain score over the 7 days preceding the visit will be calculated in the EDC system and verification of inclusion pain score \geq 4 and <9 and compliance of \geq 70% will be determined at the Enrollment Visit. Medical History will be reviewed at the Enrollment Visit for any changes. 2.

3.

Urine pregnancy test will be performed on women of child-bearing potential. Weight will be measured at the end of Part A and at the end of Part B. 4.

5.

Assessment of adverse events will be conducted after the signing of the Informed Consent. 6.

Adherence to ePRO entries will be assessed at the Enrollment Visit for inclusion. 7.

8. Adherence to diary completion will be completed at the 6M, 8M, 10M, and 12M visits.

APPENDIX B: AMERICAN DIABETES ASSOCIATION CRITERIA FOR DIAGNOSIS OF DIABETES

 $FPG \ge 126 mg/dL$ (7.0 mmol/L). Fasting is defined as no caloric intake for at least 8 hours*

OR

2-hour PG \geq 200 mg/dL (11.1 mmol/L) during OGTT. The test should be performed as described by the WHO, using a glucose load containing the equivalent of 75-g anhydrous glucose dissolved in water. *

OR

A1C \geq 6.5% (48 mmol/mol). The test should be performed in a laboratory using a method that is NGSP certified and standardized to the DCCT assay. *

OR

In a patient with classic symptoms of hyperglycemia or hyperglycemic crisis, a random plasma glucose $\geq 200 \text{ mg/dL}$ (11.1 mmol/L).

*In the absence of unequivocal hyperglycemia, results should be confirmed by repeat testing.

Note. Criteria for diagnosing diabetes Table 2.2. Referenced from "Standards of Medical Care in Diabetes 2018," American Diabetes Association, 2018, The Journal of Clinical and Applied Research and Education, V41, Supplement 1, p.S15. 2018.

1. LIST OF ABBREVIATIONS

Abbreviation	Explanation
AE	Adverse Event
ABI	Ankle-Brachial Index
BMI	Body Mass Index
CFR	Code of Federal Regulations
CRA	Clinical Research Assistant / Associate
CSR	Clinical Study Report
DSPN	Diabetic Distal Symmetric Peripheral Neuropathy
EDC	Electronic Data Capture
ePRO	Electronic Patient Reported Outcome
FCC	Federal Communication Commission
FDA	Food & Drug Administration
На	Alternative hypothesis
Но	Null hypothesis
ICH	International Conference on Harmonization
IENFD	Intraepidermal Nerve Fiber Density
IQR	Inter-Quartile Range
IRB	Institutional Review Board
ITT	Intent to Treat
MedDRA	Medical Dictionary for Regulatory Activities
NeuroQoL	Neuropathy Quality of Life Questionnaire
NCS	Nerve Conduction Studies
NPRS	Numeric Pain Rating Scale
PEMF	Pulsed Electromagnetic Field
PGI	Patient Global Impression
PP	Per Protocol
PRFE	Pulsed Radio Frequency Energy
PRN	As Needed
QA	Quality Assurance
QC	Quality Control
QST	Quantitative Sensory Testing
SAE	Serious Adverse Event
SAP	Statistical Analysis Plan
SAS	Statistical Analysis System
SPP	Skin Perfusion Pressure
TCNSS	Toronto Clinical Neuropathy Scoring System
TMF	Trial Master File
WHO Drug	World Health Organization Drug Dictionary
WPAIQ	Work Productivity and Activity Impairment Questionnaire

2. INTRODUCTION

The purpose of this Statistical Analysis Plan (SAP) is to prospectively outline the types of analyses and presentations of the data that will form the basis for conclusions regarding this clinical investigation. The analyses defined in this plan should answer the safety and effectiveness objectives outlined in the protocol, and explain in detail how the data will be handled or analyzed, adhering to commonly accepted standards and practices of biostatistical analysis in the medical device industry.

This document contains information to support the generation of a Clinical Study Report (CSR) for Clinical Protocol RBI.2017.002, including detailed descriptions of the statistical methods to be applied, as well as the analysis summary tables and figures and subject data listings intended to present the analysis results.

Provant is a medical device manufactured by Regenesis Biomedical, Inc. (Scottsdale, AZ), that has been cleared by the FDA (K972093, K091791, and K131979) for adjunctive use in the palliative treatment of post-operative pain and edema of soft tissue. The device delivers self-administered, non-thermal, non-ionizing pulsed electromagnetic energy to the target tissue, using 27.12 MHz pulses lasting 42 microseconds and delivered 1000 times per second. The system generates an electromagnetic field that is continuously monitored and regulated to ensure consistent dosing. The therapeutic electromagnetic field is delivered by means of an applicator pad that is placed against the treatment site. The device is non-invasive and does not require placement of surface or deep electrodes, nor removal of bandages or clothing.

The planned analyses identified in this SAP may be included in regulatory submissions, medical presentations and manuscripts. Exploratory analyses, not identified in this SAP, may be performed to support the clinical development program. Any post-hoc or unplanned analyses that are performed but not identified in this SAP will be clearly identified in the CSR. The structure and content of this SAP provides sufficient detail to meet the requirements identified by the FDA and the International Conference on Harmonization (ICH) Guidance on Statistical Principles for Clinical Trials.

3. STUDY OBJECTIVES AND ENDPOINTS

3.1. Study Objectives

The primary objective of this study is to demonstrate the analgesic efficacy of PEMF treatment compared to sham treatment in patients with painful diabetic distal symmetric peripheral neuropathy (DSPN).

3.1.1. Efficacy Assessments and Endpoints

There will be 11 total endpoints from Part A of the protocol (Part B analysis is in a separate SAP); the interest will be in the change from baseline and the differences between active Provant therapy vs. sham.

Primary Endpoint: Absolute change from baseline in pain intensity as measured by the 11-point, numerical pain rating scale (NPRS) (0-10; where 0=no pain, to 10=worst possible pain) through 4 months.

Secondary Endpoint 1: Percentage of patients who have either a 2 point or 30% reduction in NPRS at 4 Months.

Secondary Endpoint 2: Time to 30% or 2-point reduction in NPRS, whichever comes first at 4 Months.

Secondary Endpoint 3: Change in neuropathy related quality of life (NeuroQoL) between baseline and end of treatment at 4 Months.

Secondary Endpoint 4: Changes in Skin Perfusion Pressure (SPP) from baseline to end of treatment at 4 Months.

Secondary Endpoint 5: Changes in Nerve Conduction Studies (NCS) of Velocity and/or Amplitude between baseline and end of treatment at 4 Months.

Secondary Endpoint 6: Changes in Quantitative Sensory Testing (QST) between baseline and end of treatment at 4 Months.

Secondary Endpoint 7: Change in Patient Global Impression (PGI) at 4 Months.

Exploratory Endpoint 1: Change in Work Productivity and Impairment Questionnaire (WPAIQ) **Exploratory Endpoint 2:** Changes in intraepidermal nerve fiber density (IENFD) at the distal thigh.

Exploratory Endpoint 3: Changes in IENFD at the distal leg.

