All hypothesis tests comparing active and sham treatment will be two-sided and conducted at the 5% significance level based on Part A of the study. The primary population for assessing efficacy and safety will be the ITT population from Part A. A secondary analysis of the individual efficacy endpoints will be conducted using the Per-Protocol population from Part A. All summary tables will be presented by treatment group and over all patients in the analysis population being summarized. Continuous variables will be summarized using the following descriptive statistics: n, mean, SD, median, minimum, and maximum. Categorical variables will be summarized using counts and percentages. Percentages presented will be calculated using all patients in the analysis population being summarized (with randomized or received treatment as/if appropriate) as the denominator.

To compare the absolute change in pain from baseline to 4months, the intra-patient change will be calculated and serve as the dependent variable in the analysis. The baseline pain score will be introduced in the model as a covariate. Clinical site will be added to the model to assess poolability of the data across sites. Interaction between clinical site and treatment will be evaluated using a type 1 error rate of 10%.

Treatment-emergent adverse events will be summarized by study part, type, frequency, severity, and relationship to the study device. Adverse events will be provided in a listing.

SAS® Version 9.4 or later will be used to produce all statistical tables, listings and figures to be contained in the integrated statistical/clinical report.

Table of Contents

1.	INTRODUCTION AND BACKGROUND	.19
2.	STUDY OBJECTIVES	.24
3.	STUDY DESIGN	.25
3.1	Study Design	. 25
3.2.	EFFICACY ENDPOINTS	.26
3.3	SAFETY EVALUATION	.26
3.4	Eligibility Criteria	. 27
3.5	ENROLLMENT	. 30
3.6	RANDOMIZATION	. 30
3.7	DEVICE DESCRIPTION	. 30
3.7.1	Control Unit	. 30
3.7.2	Treatment Applicator	. 32
3.8	LOGISTICS AND DEVICE ACCOUNTABILITY	. 32
3.9	LABELING	. 33
3.10	Preparation and Administration	. 33
3.11	Blinding	. 33
3.12	Study Assessments	. 34
3.12.1	Primary Efficacy Assessment	. 34
3.12.2	Secondary Efficacy Assessments	. 34
3.12.3	Exploratory Efficacy Assessment	.37
3.12.4	Additional Study Assessments	. 38
3.12.5	Safety Assessments	. 40
4.	STUDY PROCEDURES	.40
4.1	VISIT 1 – SCREENING VISIT (DAY -15)	.40
4.2	14-Day Run-In Period	.42
4.3	Visit 2 – Enrollment Visit (Day 0)	.42
4.4	Day 7 Phone Call (Day 7 +2 Days)	.43

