3.12.2 Secondary Efficacy Assessments

NeuroQoL

The NeuroQoL is a validated 29 question assessment tool that measures the effects of diabetic peripheral neuropathy and its complications on an individual's quality of life. Subjects are asked about the effect their foot problems may have on their daily life and well-being in the past 4 weeks, with "foot problems" meaning lost or reduced feeling in the lower extremities, pain discomfort, and in some cases unsteadiness while walking or standing. The questionnaire will be completed by the

35

subject at the Enrollment Visit, Month 2, Month 4, Month 8, and Month 12 visit (Day 361).

Skin Perfusion Pressure

Vasamed Sensilase PAD-IQ measures the perfusion pressure (in mmHg) of microcirculation using a laser Doppler sensor. SPP uses the reactive hyperemia to assess capillary health in specific angiosomes. Two previous trials were conducted in patients with painful peripheral diabetic neuropathy showing an increase in circulation (pressure) from baseline.

The patient lies down in supine position and remains silent and still. The Laser Sensor Assembly (LSA) is inserted into the LSA Placement Guide and the optical sensor window is oriented toward the skin on the foot. A cuff is positioned so that the LSA is centered on the bladder both horizontally and vertically. The pressure of the cuff is then automatically increased to a pressure necessary to occlude blood flow and then released at a controlled rate and a measurement of the pressure in the angiosome is made. Skin Perfusion Pressure- SPP is the pressure required for restoring microcirculatory blood flow following release of carefully controlled occlusion. Two measurements are obtained per foot; one on the dorsal aspect of each foot in the distribution of the dorsalis pedis artery angiosome and on the plantar aspect of each foot in the distribution of the lateral plantar artery angiosome. SPP will be conducted at the Enrollment Visit to obtain a baseline value and at months 2, and 4. An increase in SPP would be considered clinically meaningful.

Sural Nerve Conduction Studies (NCS)

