Sural Nerve Conduction Studies (NCS) assess large myelinated axons. Using the NC-stat[®] DPNCheck[®], the subject will assume a comfortable position so that their right or left leg is visible (that the subject's outer ankle bone and Achilles tendon are visible). The patient preparation pad is then used to thoroughly clean the subject's outer lower leg and ankle bone area to remove any residue. The subject's lateral malleolar (ankle) bone is then identified to align the anode and cathode just behind with the cathode just adjacent to the middle of the ankle bone. The device is aligned on the calf pressing firmly down on the foam to ensure contact on either side of the calf. The sural nerve conduction velocity and amplitude will be recorded. The test will then be repeated on the opposite leg. NCS will be collected at the Enrollment Visit to obtain a baseline value and at Days 121 (month 4) and 361 (month 12). An increase in velocity and/or an increase in amplitude would suggest DPN improvement.

Quantitative Sensory Testing (QST)

Quantitative Sensory Testing (QST) for thermal sensation assesses small diameter unmyelinated and lightly myelinated axons. QST is a noninvasive technique providing an easy to use, validated measure of warm, cool, and heat pain thermal sensory thresholds.

The Thermal Stimulator is placed on the surface of the skin on the dorsal aspect of the foot. The Thermal Stimulator is held in place on the foot by a Velcro strap, which wraps around the subject's foot.

Contact thermal stimulation will be delivered using the Medoc Ltd. Q-Sense system. A Thermal Stimulator probe ("thermode") is placed on the surface of the skin on the dorsal aspect of the foot in the distribution of the superficial branch of the distal fibular (peroneal) nerve. The probe is held in place by a Velcro strap, which wraps around the subject's foot. Using a Patient Response Unit (PRU), the subject presses a button to identify their response to the delivered thermal stimulation. This is done by successful trials to assess cool sensation threshold (CS), warm sensation threshold (WS) and heat pain threshold (HP) modalities using the method of Limits. Within the cool and warm sensation modalities, the trial is repeated 4 times on each foot and 3 times on each foot for heat pain threshold modality. The cool thermal testing should be conducted prior to the warm and heat pain thermal testing.

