- If the patient discontinues due to an AE lack of response, then missing data will be assumed to follow a distribution similar to the baseline values observed in the patient's randomized treatment.
- If the patient discontinues due to reasons other than AE or treatment response, at each time point, missing data will be assumed to follow a distribution similar to scores for patients that are still in the study and randomized to the same treatment group.

Results of the 120-day results, and the MMRM using the multiply imputed data, will be summarized using the SAS MIANALYZE procedure.

A hierarchical approach will be undertaken for the pre-specified secondary outcomes. Testing will occur in the listed sequence following testing of the primary endpoint.

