The Level 3 displays will report the paired results for the change from the baseline through Month 4. For example, if 18 subjects complete the baseline evaluation and 16 subjects complete the Month 4 visit, the difference (Month 4 minus Baseline) will contain 16 subjects.

Supportive individual subject data listings will be sorted and presented by subject number and visit date, if applicable. Listings will also include the number of days relative to the initial study treatment (active or sham).

Specific algorithms are discussed for imputing missing or partially missing dates, if deemed appropriate, under specific data topics. Imputed or derived data will be flagged in the individual subject data listings. Imputed data will not be incorporated into any raw or primary datasets. The imputed data will be retained in the derived / analysis datasets.

The total duration for a subject *on-study* will be calculated as the difference between the date of initial study treatment (active or sham) and the last day of observation plus 1 day. All calculations for defining the duration on-study will follow the algorithm DURATION = [STUDY COMPLETION OR WITHDRAW DATE – INITIAL TREATMENT DATE + 1].

This section details general conventions to be used for the statistical analyses. The following conventions will be applied to all data presentations and analyses.

- Summary statistics will consist of the count and percentage in each level for categorical variables, and the sample size (n) mean, median, standard deviation (SD), minimum, and maximum values for continuous variables.
- All mean and median values will be formatted to one more decimal place than the measured value. Standard deviation values will be formatted to two more decimal places

than the measured value. Minimum and maximum values will be presented with the same number of decimal places as the measured value.

- The number and percentage of responses will be presented in the form XX (XX.X%).
- All probability values will be rounded to four decimal places. All p-values that round to 0.0000 will be presented as '<0.0001' and p-values that round to 1.0000 will be presented as '>0.9999'. P-values <0.05 will be considered to be statistically significant.
- All summary tables will include the analysis population sample size (i.e., number of subjects).

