14.4.1.2.1a	Summary of the Efficacy Endpoints by Randomized Treatment Assignment and Time - NeuroQol (Unweighted) Domain 1: Pain
14.4.1.2.2	Summary of the Efficacy Endpoints by Randomized Treatment Assignment and Time - NeuroQol (Weighted) Domain 2: Lost/reduced feeling
14.4.1.2.2a	Summary of the Efficacy Endpoints by Randomized Treatment Assignment and Time - NeuroQol (Unweighted) Domain 2: Lost/reduced feeling
14.4.1.2.3	Summary of the Efficacy Endpoints by Randomized Treatment Assignment and Time - NeuroQol (Weighted) Domain 3: Diffuse sensory-motor symptoms
14.4.1.2.3a	Summary of the Efficacy Endpoints by Randomized Treatment Assignment and Time - NeuroQol (Unweighted) Domain 3: Diffuse sensory-motor symptoms
14.4.1.2.4	Summary of the Efficacy Endpoints by Randomized Treatment Assignment and Time - NeuroQol (Weighted) Domain 4: Restrictions in activities of daily living
14.4.1.2.4a	Summary of the Efficacy Endpoints by Randomized Treatment Assignment and Time - NeuroQol (Unweighted) Domain 4: Restrictions in activities of daily living
14.4.1.2.5	Summary of the Efficacy Endpoints by Randomized Treatment Assignment and Time - NeuroQol (Weighted) Domain 5: Disruptions in social relationships
14.4.1.2.5a	Summary of the Efficacy Endpoints by Randomized Treatment Assignment and Time - NeuroQol (Unweighted) Domain 5: Disruptions in social relationships
14.4.1.2.6	Summary of the Efficacy Endpoints by Randomized Treatment Assignment and Time - NeuroQol (Weighted) Domain 6: Emotional distress
14.4.1.2.6a	Summary of the Efficacy Endpoints by Randomized Treatment Assignment and Time - NeuroQol (Unweighted) Domain 6: Emotional distress
14.4.1.3	Summary of the Skin Perfusion Pressure Results by Randomized Treatment Assignment and Time
14.4.1.4	Summary of the Nerve Conduction Results by Randomized Treatment Assignment and Time
14.4.1.5	Summary of the QST Results by Randomized Treatment Assignment and Time
14.4.1.6	Summary of the Work Productivity and Activity Impairment Questionnaire (WPAIQ) by Visit and Randomized Treatment Assignment
14.4.1.7	Summary of the Patient Global Impression (PGI) by Visit and Randomized Treatment Assignment
14.4.1.8	Summary of Treatment Satisfaction by Visit and Randomized Treatment Assignment
14.4.1.10	Summary of the Toronto Clinical Neurpathy Scoring System by Randomized Treatment Assignment and Time

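### Secondary Endpoint 5 (nerve conduction) can be read as met by either velocity or amplitude, so its step in the testing sequence does not hold 5%; Endpoints 3, 4, 6 and 7 name no single tested variable

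*SAP*

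**What the plan says.** **The sequence.** Protocol 7.1 sets a hierarchical approach for the secondary outcomes: "Testing will occur in the listed sequence following testing of the primary endpoint". The Protocol synopsis (Statistical Considerations) makes all active-versus-sham tests "two-sided and conducted at the 5% significance level". SAP 7 adds: "P-values <0.05 will be considered to be statistically significant". SAP 7.3, however, applies no multiplicity adjustment to any endpoint and does not mention the sequence.

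**Endpoint 5.** SAP 3.1.1 defines it as "Changes in Nerve Conduction Studies (NCS) of Velocity and/or Amplitude between baseline and end of treatment at 4 Months", and the Protocol synopsis carries the same and/or. Protocol 3.12.2 interprets it: "An increase in velocity and/or an increase in amplitude would suggest DPN improvement". Both measures are taken on both legs.

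**The other endpoints from 3 to 7:**
- Endpoint 3, NeuroQoL: the SAP 11 table list has six domains, each weighted and unweighted (for example "NeuroQol (Unweighted) Domain 1: Pain"), plus a table by question. No total score is listed.
- Endpoint 4, skin perfusion pressure (SPP): "Two measurements are obtained per foot", one dorsal and one plantar, on both feet.
- Endpoint 6, quantitative sensory testing (QST): trials "to assess cool sensation threshold (CS), warm sensation threshold (WS) and heat pain threshold (HP) modalities", on each foot.
- Endpoint 7, Patient Global Impression (PGI): three questions (Protocol 3.12.2).

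For none of these five do the documents name a deciding component, a composite, a rule for combining left and right, a requirement that all components succeed, or a division of alpha within the step.

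**The concern.** A fixed sequence keeps its error rate because each step is a single pass-or-fail test at the full 5%. If a step can be passed on the better of two results, each read against 0.05, it is passed too often when there is no effect. A false pass at Endpoint 5 also opens Endpoint 6.

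The physiological endpoints are a likely source of claims. Protocol 1 reports that the earlier exploratory study saw better skin perfusion pressure and nerve conduction velocity but no consistent change in pain scores. SAP 2 expects the planned analyses to be used in regulatory submissions and manuscripts.

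**Working it through.** **Inputs from the documents.** Two-sided alpha of 0.05 per test (Protocol synopsis; SAP 7). Components of Endpoint 5: k = 2 (SAP 3.1.1). Possible components elsewhere, from Protocol 3.12.2 and SAP 11: NeuroQoL 6 domains; SPP 2 sites, or 2 × 2 = 4 with feet kept apart; QST 3 thresholds, or 3 × 2 = 6 with feet kept apart; PGI 3 questions. Nerve conduction with legs kept apart would give 2 × 2 = 4.

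**Input assumed.** The correlation r between component test statistics is not in the documents. I take it as equal across components and vary it from 0 to 0.9.

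**Step 1: the plan's own figure.** With one test per step, 1 − 0.95 = 5%. This reproduces the stated level.

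**Step 2: any of k components suffices, independent.** P = 1 − 0.95^k.
- k = 2: 1 − 0.9025 = 9.8%
- k = 3: 1 − 0.8574 = 14.3%
- k = 4: 1 − 0.8145 = 18.5%
- k = 6: 1 − 0.7351 = 26.5%

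**Step 3: equal correlation r.** With c = 1.96 and X standard normal, P = 1 − E{[Φ((c − √r·X)/√(1−r)) − Φ((−c − √r·X)/√(1−r))]^k}, evaluated numerically:

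| k | Where it could arise | r = 0 | r = 0.5 | r = 0.8 |
|---|---|---|---|---|
| 2 | Endpoint 5, legs averaged (and/or as written) | 9.8% | 9.1% | 7.8% |
| 3 | QST with feet averaged; PGI | 14.3% | 12.5% | 9.8% |
| 4 | SPP with feet apart; nerve conduction with legs apart | 18.5% | 15.6% | 11.4% |
| 6 | NeuroQoL domains; QST with feet apart | 26.5% | 20.7% | 13.9% |

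At r = 0.9, k = 2 still gives 7.0%. SPP with feet averaged would also have k = 2. Only the first row rests on wording in the plan; the others show what would follow if any component were allowed to count.

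**Step 4: results favouring active only.** Against a nominal 2.5%, k = 2 gives 4.9%, 4.5% and 3.9% at r = 0, 0.5 and 0.8, and k = 6 gives 14.1%, 10.4% and 6.9%.

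**Step 5: condition.** These are rates for a step that has been reached and whose endpoint has no true effect. Under the Protocol sequence, Endpoint 5 is reached only after the primary endpoint and Endpoints 1 to 4 have passed.

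**Step 6: possible repairs for two components.** One named variable: 5%. Both required at 0.05: at most 5%. Alpha split 0.025 each: 1 − 0.975² = 4.9% if independent, and at most 5% in any case.

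**The case against.** The strongest reply is that the plan describes measurements, not success rules. SAP 11 writes out a hypothesis only for the pain score. Its entries for NeuroQoL, SPP, nerve conduction and QST are summary tables, and the Level 3 layout in SAP 7 shows no p-value row. The code in SAP 13.2 is generic, with a note that some of it may go unused. The Protocol sentence on velocity and amplitude can be taken as clinical interpretation. This is fair as far as it goes, but Protocol 7.1 does commit to testing these endpoints in order, so each needs a decision rule. The only wording that bears on one, for Endpoint 5, is and/or.

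Several stronger readings are tempting and are not supported:
- *That any component of NeuroQoL, SPP or QST may win its step.* The documents are silent; only nerve conduction has and/or wording.
- *That every component on every side is a planned test, or that weighted and unweighted domains count as separate tests.* The counts above are possible, not planned, and weighted and unweighted versions of a domain should be highly correlated.
- *That left and right will be analysed apart and precision lost.* The documents say both sides are measured but not how they are combined.
- *That a per-subject rule of either measure rising would create false responders.* No such responder is defined, and noise would produce them equally in both arms.

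Two further points stand. If the treatment has no effect on anything, the primary test already limits the chance of getting further to about 5%, so the inflation matters where pain responds and the later endpoint does not. And if SAP 7.3 governs, there is no sequence to protect; that conflict has to be settled as well, but restoring the sequence would not by itself give Endpoints 3 to 7 one test each.

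**Conclusion.** The concern holds for Endpoint 5 as worded: read as met by either measure, its step runs at 7.0% to 9.8% instead of 5% over correlations from 0.9 down to 0. The size depends on the assumed correlation; for any correlation short of perfect the direction does not.

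For Endpoints 3, 4, 6 and 7 the finding is an omission: no single tested variable is named, so the same route is open but not stated. If it were taken, three to six components would give roughly 10% to 27% over correlations from 0.8 down to 0. The primary endpoint and Secondary Endpoints 1 and 2 are not affected.

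**What to change.** Before unblinding, change the Protocol (synopsis endpoints and 7.1) and SAP 3.1.1 and 11 together, since editing only one would create a new mismatch:

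1. Give each of Endpoints 3 to 7 one subject-level tested variable and one p-value. Where both sides are measured, average left and right.
2. Where several components remain, let the sponsor name one, or pre-specify a composite and state its direction of benefit. For NeuroQoL, also state whether the tested score is weighted or unweighted. For QST, state the direction for each threshold, which the documents do not give.
3. In Endpoint 5, replace and/or with the named variable. Alternatively require both measures, or split alpha within the step. If alpha is split, also state how much passes on when only one measure succeeds. If one measure truly works and the full 5% is carried forward, the chance of a false claim from the other measure or the next endpoint could reach 1 − 0.975 × 0.95 = 7.4% under independence.
4. Report all other components descriptively.
5. Reconcile this with SAP 7.3, so that both documents state whether the sequence applies.

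The cost is a Protocol and SAP wording change with no new data. The downside is that a component that moves alone can only be described; requiring both nerve conduction measures would also lower power for that step.
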